#### **4.4.3      Investigational Medicinal Product Accountability**

IMP (RO7020531) and placebo required for completion of this study will be provided by the Sponsor. The investigational site will acknowledge receipt of IMPs, to confirm the shipment condition and content. Any damaged shipments will be replaced.

The Investigator is responsible for the control of drugs under investigation. Adequate records of the receipt (e.g., Drug Receipt Record) and disposition (e.g., Drug Dispensing Log) of the study drug must be maintained. The Drug Dispensing Log must be kept current and should contain the following information:

- The identification of the healthy volunteer to whom the study drug was dispensed (for example healthy volunteer initials and date of birth).
- All records and drug supplies must be available for inspection by the Roche Monitor [at every monitoring visit].

IMPs will either be disposed of at the study site according to the study site's institutional standard operating procedure or returned to the Sponsor with the appropriate documentation. The site's method of IMP destruction must be agreed upon by the Sponsor. Local or institutional regulations may require immediate destruction of used investigational medicinal product for safety reasons. In these cases, it may be

acceptable for investigational study site staff to destroy dispensed investigational product before a monitoring inspection provided that source document verification is performed on the remaining inventory and reconciled against the documentation of quantity shipped, dispensed, returned, destroyed and provided that adequate storage and integrity of drug has been confirmed.

The site must obtain written authorization from the Sponsor before any IMP is destroyed, and IMP destruction must be documented on the appropriate form.

Written documentation of destruction must contain the following:

- Identity of investigational product destroyed.
- Quantity of investigational product destroyed.
- Date of destruction.
- Method of destruction.
- Name and signature of responsible person (or company) who destroyed investigational products.

Accurate records of all IMPs received at, dispensed from, returned to, and disposed of by the study site should be recorded on the Drug Inventory Log.

## **4.5 CONCOMITANT THERAPY, DIETARY AND SPECIAL REQUIREMENTS**

### **4.5.1 Permitted Therapy**

As a general rule, no concomitant medication (including health supplements, vitamins or herbal remedies) will be permitted, unless the rationale for use is discussed between the Investigator and Sponsor and is clearly documented. The following medications are exceptions:

- Medications used to treat an AE may only be prescribed after consultation with the Sponsor (with the exception of acetaminophen/paracetamol), unless there is a medical need to ensure the well-being of the subject that should not be delayed. All therapy and/or medication administered to manage AEs should be recorded on the AE electronic case report form (eCRF).
- Hormone replacement therapy (HRT), continue using if initiated two months prior to study start.
- Acetaminophen/paracetamol is allowed up to a maximum dose of 2 g per day. During the period of confinement to the clinical research unit, subjects will be restricted from the use of acetaminophen/paracetamol and other non-prescription medications beginning 4 hours prior to dosing through 4 hours after dosing unless deemed necessary to treat an AE by the Investigator.

All medications (prescription drugs, over-the-counter [OTC] drugs, approved dietary and herbal supplements, nutritional supplements) taken within 4 weeks of study screening will be recorded on the appropriate eCRF.

#### **4.5.2 Prohibited Therapy**

Use of the following therapies is prohibited:

- Any prescribed or OTC medications (except for the cases given in Section 4.5.1), including health supplements, vitamins or herbal remedies within 5 half-lives or 2 weeks, whichever is longer, prior to the first dosing until the follow-up visit.
- Any systemic anti-neoplastic (including radiation) or immune-modulatory treatment (including systemic oral or inhaled corticosteroids, IFN or PEG-IFN) within 6 months prior to the first dose of study drug until the follow-up visit (Day 8 for SAD and Day 20 for MAD). Eye drop-containing and infrequent inhaled corticosteroids are prohibited from 4 weeks prior to the first dose of study drug until the follow up visit.

#### **4.5.3 Dietary and Special Requirements**

There are data suggesting that concentrated green tea (including bottled green tea beverages) may inhibit aldehyde oxidase ([Tayama et al 2011](#)). Therefore, subjects should minimize the amount of bottled green tea beverages and other green tea preparations they drink from Day –7 until the follow-up visit at Day 8.

Subjects must fast overnight (at least 10 hours) before the dosing and must not eat for 4 hours after the dose is administered. Approximately 4 hours after dosing, subjects will be administered lunch.

Water will be allowed ad libitum until one hour prior to dosing and from one hour post-dosing. However, the excessive consumption of fluids (greater than 3 liters per day) should be avoided until completion of the follow-up visit.

Laboratory safety assessments should be conducted after subjects have been fasted for a minimum of 8 hours.

Alcohol must not be consumed from 48 hours before screening, 48 hours before admission until discharge from the clinic, and 48 hours before each scheduled visit. Please refer to [Appendix 8](#) for the calculation of alcohol standard drinks as relates to eligibility criteria.

Caffeine (i.e., beverage, chocolate or supplements) must not be consumed from 48 hours prior to study drug administration until discharge from the clinic.

Strenuous exercise is not permitted during the study from 96 hours before admission until completion of the follow-up visit.

The use of tobacco is not permitted from Day -2 till Day 3 for the SAD part and from Day -2 till Day 14 for the MAD part of the study.

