until a consensus agreement is reached between the Sponsor and the Investigator; the Ethics Committee will be informed. RO7020531 doses planned for this study in Chinese healthy volunteers will not be evaluated if they are expected to result in RO7011785 exposures which are not found to be safe and tolerable in the global EIH study. In addition, doses will not be escalated in both the SAD and MAD if stopping rules have been met (see Section 3.1.3). Safety and tolerability at each dose level will determine eligibility for dose escalation. Measurement of PK and select PD markers will be made with each cohort and, upon availability, will be utilized along with safety data to determine the first dose with which to initiate the MAD. The MAD part of this study may be initiated before the SAD part is completed. Therefore, both SAD and MAD parts of this study may run in parallel.

In the SAD cohorts, subjects will be screened up to 28 days before randomization and asked to remain in the unit from Day – 2 until Day 3 with dosing occurring on Day 1. After being discharged on Day 3, subjects will return for an outpatient visit on Day 5 and a follow-up visit on Day 8. All subjects will have a follow-up phone call 28 days after the study drug administration. Subjects will be asked to report any AEs that occur during this period.

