### **3.1.1.2      Multiple Ascending Dose Study**

The trigger to start the first cohort in the MAD includes documentation of adequate safety and tolerability in the SAD cohorts and evidence of PD effects. For a given dose evaluated in the SAD, evidence in at least two subjects exhibiting responses above placebo-defined baseline for select PD biomarkers, including *the protein and metabolite markers IFN- $\alpha$ , IP-10, TNF- $\alpha$ , IL-6, IL-10, IL-12p40 and neopterin and markers of transcriptional responses (ISG15, OAS-1, MX1 and TLR7)*, should be demonstrated. If the next dose in the SAD has been considered safe, then the previous dose demonstrating TLR-associated PD activity will be considered as the starting dose for the MAD. In addition, the starting dose/exposure in the MAD part of this study should have been considered safe in the global EIH study (NP39305). Only doses covered by the dose range evaluated in the SAD part will be used in the MAD, and two to three dose levels will be evaluated (Figure 1).

[figure not shown]
Once criteria have been reached to determine an initial dose for MAD, subjects will be screened up to 28 days before enrollment into the MAD part of this study. They will be asked to remain in the unit from Day -2 until Day 14 with QOD dosing initiated on Day 1. In total, 7 QOD doses will be administered with the last dose given on Day 13. Subjects will be discharged on Day 14. After completing 7 QOD doses, each subject in the MAD cohorts will return for an outpatient follow-up visit 7 days after the last dose. All subjects will have a follow-up phone call 28 days after their last dose. Subjects will be asked to report any AEs that occur during this period.

Upon safety review of the MAD cohort(s) data, dose escalation will proceed in the MAD part of this study. The maximum dose investigated in MAD will not exceed doses

evaluated in the SAD part of this study nor will it exceed doses and exposures considered to be safe and with acceptable tolerability in the global EIH study.

Based on the PK, PD and safety evaluation of the previous dose cohorts, additional cohorts of subjects may be enrolled at higher or lower dose levels, or at a dose level already tested.

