### **4.6.2.3      Follow Up Assessments**

Healthy volunteers who complete the study (SAD and MAD parts) or discontinue from the dosing early (MAD part only) will be asked to return to the clinic approximately 7 days ( $\pm 1$  day) after the last dose of study drug for a follow-up visit and will be contacted for a follow-up call approximately 21 days ( $\pm 3$  days) after the follow-up visit to complete assessments as specified in the SoA ([Appendix 1](#), [Appendix 2](#), [Appendix 3](#) and [Appendix 4](#)). After the follow-up call, adverse events should be followed as outlined in Section [5.5](#), Section [5.6](#).

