### **Appendix 3 Schedule of Assessments: MAD (cont.)**

- a) A follow-up visit to be completed 7 days ( $\pm 1$ ) after the last dose of study medication.
- b) A follow-up call to be completed 28 days ( $\pm 3$ ) after the last dose of study medication.
- c) Full physical examination, including recording of weight, is required at Screening, Day – 1 and Follow-Up visit. At all other visits (or as clinically indicated), limited, symptom-directed physical examinations should be performed at the discretion of the Investigator. Height will only be recorded at Screening. BMI will be calculated at Screening.
- d) Vital signs include blood pressure, pulse rate, respiratory rate and body temperature. Blood pressure, respiratory rate and pulse rate will be obtained after the subject has been in a supine *or sitting* position for at least 5 minutes. Blood pressure measurement will be performed in triplicate (can be as short as 20-second to 1-minute interval between measurements). Pulse rate and body temperature measurement will be performed as single assessments.
- e) 12-lead ECGs will be obtained in triplicate (three consecutive interpretable 12-lead ECGs within a 2-5 minute interval) after the subject has been in a supine position for at least 10 minutes. Automated ECG intervals (PR (PQ), QRS, QT, QTcF) and HR will be captured or calculated, and the changes in T-wave and U-wave morphology will be documented.
- f) Serum or plasma beta-human chorionic gonadotropin ( $\beta$ -HCG) at Screening, urine on all other occasions (females only).
- g) Study drug will be administered in fasted state (after an overnight fast of at least 10 hours).
- h) Subjects will be admitted to the unit on Day – 2 to start time-matching ECG assessments in the morning of Day – 1. Subjects will stay in the unit till Day 14, with the first dose given on Day 1 and last dose given on Day 13.
- i) Follicle-stimulating hormone (females only to confirm post-menopausal status, performed at screening only).
- j) At Screening and Day – 1 only (drugs of abuse urine test and alcohol test).
- k) If the clinical genotyping blood sample is not collected at Day 1, it may be collected at any time during the conduct of the clinical study.
- l) At Screening, Day – 2 and Day – 1, only serious adverse events caused by a protocol-mandated intervention should be reported.

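### Does the green-tea advice lapse on Day 8, in the middle of dosing, for subjects in the multiple-dose part?

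*Combined protocol and SAP*

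**What the plan says.** Section 4.5.3 explains that concentrated green tea may inhibit aldehyde oxidase. It asks subjects to keep their intake low from Day -7 "until the follow-up visit at Day 8". The sentence does not separate the SAD part from the MAD part.

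The follow-up visit is set elsewhere:

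- Section 4.6.2.3 covers both parts and places it about 7 days (±1 day) "after the last dose of study drug for a follow-up visit".
- Section 3.1.1.1 (SAD): "subjects will return for an outpatient visit on Day 5 and a follow-up visit on Day 8".
- Section 3.1.1.2 (MAD): subjects "return for an outpatient follow-up visit 7 days after the last dose".
- Section 4.5.2 gives both days for the ban on immune-modulatory and anti-neoplastic treatment: "until the follow-up visit (Day 8 for SAD and Day 20 for MAD").
- Appendix 3, footnote h (MAD): "Subjects will stay in the unit till Day 14, with the first dose given on Day 1 and last dose given on Day 13".

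Two other limits in Section 4.5.3 also run to the follow-up visit but name no day. Excess fluid "should be avoided until completion of the follow-up visit", and strenuous exercise is not allowed "from 96 hours before admission until completion of the follow-up visit".

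**The concern.** For a MAD subject, the green-tea sentence names a visit and a day that do not coincide. Day 8 of the MAD is an in-clinic day between the doses of Day 7 and Day 9. If a reader took the day as binding, the advice would stop partway through dosing.

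The stake would be pharmacokinetic. Section 1.2.1 reports that aldehyde oxidase is one of two pathways that convert the prodrug to the active metabolite RO7011785. Section 3.2.3 compares the intensive profiles after the first dose and after the Day 13 dose to see whether PK changes with repeated dosing. A dietary inhibitor that was limited at the first profile but not at the second would be an unwanted difference between the two.

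**Working it through.** **Reproducing the protocol's visit days.** Follow-up day = last dose day + 7.

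- SAD: last dose Day 1, so 1 + 7 = Day 8. This matches Section 4.5.2.
- MAD: seven every-other-day doses fall on Days 1, 3, 5, 7, 9, 11 and 13, so 13 + 7 = Day 20. This also matches Section 4.5.2.

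**Size of the mismatch for a MAD subject who completes dosing.** 20 - 8 = 12 days. The ±1 day window gives 19 - 8 = 11 to 21 - 8 = 13 days, so the window cannot explain it.

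**What each reading implies in the MAD.**

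| | Visit governs (Day 20) | Day governs (Day 8) |
|---|---|---|
| Doses after the end-point | 0 of 7 | 3 of 7 (Days 9, 11, 13) |
| Intensive PK profiles after it | 0 of 2 | 1 of 2 (Days 13-14) |

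**Which reading the text supports.** The end-point named is a visit, and the day describes it. The MAD schedule in Appendices 3 and 4 has no follow-up visit on Day 8, so the day reading works only if the word for the visit is ignored. Section 4.5.2 attaches the same visit to Day 8 in the SAD and Day 20 in the MAD. The fluid and exercise limits in Section 4.5.3 also end at the visit.

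**What is left uncovered if the day governs.**

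1. MAD subjects stay in the unit until Day 14 (Section 3.1.1.2; Appendix 3, footnote h).
2. Section 4.5.3 bars caffeine, including in beverages, from 48 hours before dosing until discharge. If ordinary green tea counts as a caffeine beverage, it is barred through Day 14.
3. Section 4.5.2 bars health supplements and herbal remedies until the follow-up visit, with no day attached to that item. Green tea taken in those forms would plausibly stay barred to Day 20.
4. The last plasma PK sample is the 24-hour sample on Day 14 (Appendix 4). Green tea drunk between discharge and Day 20 (20 - 14 = 6 days) cannot reach any PK sample.

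The remainder is caffeine-free green tea drunk in the unit on Days 9 to 14. Section 4.5.3 only asks that intake be kept low, so such drinks are not forbidden outright under either reading.

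**The case for a change.** The best case for acting is that the error is in the current text and that no other passage gives a green-tea end day for the MAD. Section 4.5.3 itself separates the two parts in its tobacco rule, so the omission stands out. The sponsor also treats aldehyde oxidase as relevant to exposure: Section 6.8 plans to examine its polymorphisms against PK and PD. Advice needs one identifiable end-point even when it is only advice, and the correction would take one phrase.

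Most of this stands as description. Day 8 is the wrong number for the MAD on either reading. What does not follow is that the slip matters to the trial. The visit is identifiable from the section directly before. The counts of 3 doses and 1 profile arise only on the less natural reading, and they describe wording, not exposure. The documents give no effect size for green tea and do not show that caffeine-free green tea would be available in the unit. Low cost alone is not a reason to change the plan when no result would differ.

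**Conclusion.** This is a clerical slip: a SAD day number left in a sentence that also applies to the MAD. The named visit and the named day differ by 12 days for MAD completers. On the natural reading the visit governs and the advice covers all 7 doses and both intensive profiles. On the other reading, the gap is at most caffeine-free green tea in the unit on Days 9 to 14.

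No change to the plan follows. No bias is shown, and there is no identified effect on the safety, PK or PD summaries or on dose decisions. The conclusion rests on two points: staff take the visit day from Section 4.5.2 and the MAD schedule, and, for the fallback reading only, ordinary green tea counts as a caffeine beverage. The documents do not state the second point. If it failed, the uncovered item on the day reading would be green tea drinks generally in the unit on Days 9 to 14, but the natural reading would be unaffected.

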## **4.6 STUDY ASSESSMENTS**

### **4.6.1 Description of Study Assessments**

All examinations listed below will be performed according to the Schedule of Assessments (SoA) outlined in [Appendix 1](#), [Appendix 2](#), [Appendix 3](#) and [Appendix 4](#).

At time-points when several pre-dose assessments coincide, the following sequence should be followed:

- Urine collection (urinalysis, urine PK pre-dose sample).
- ECG recordings.
- Vital signs.
- Pre-dose blood sampling (pre-dose PK, pre-dose PD, exploratory samples, safety blood tests).
- RO7020531/placebo intake.

For the post-dose assessments, the following sequence should be followed with the PK blood sample (or PD blood sample if there is no PK sampling) to be taken at the nominal time-point:

- ECG recordings.
- Vital signs.
- Post-dose blood sampling (post-dose PK, post-dose PD).

#### **4.6.1.1 Medical History and Demographic Data**

Medical history includes clinically significant diseases, surgeries, reproductive status, smoking history, use of alcohol and drugs of abuse and all medications (e.g., prescription drugs, OTC drugs, herbal or homeopathic remedies, nutritional supplements) used by the healthy volunteer within 4 weeks prior to the screening visit.

Demographic data will include age, sex, and self-reported race/ethnicity.

#### **4.6.1.2 Physical Examinations**

A complete physical examination should be performed at time-points indicated in the SoA ([Appendix 1](#), [Appendix 2](#), [Appendix 3](#) and [Appendix 4](#)) and includes an evaluation of the head, eyes, ears, nose, throat, neck and lymph nodes, and the cardiovascular, dermatological, musculo-skeletal, respiratory, GI and neurological systems. A genitourinary examination may be performed in case of evocative symptoms at the Investigator's discretion. Any abnormality identified at Screening or at baseline should be recorded on the Medical History eCRF.

At subsequent visits (or as clinically indicated), limited, symptom-directed physical examinations should be performed. Changes from baseline abnormalities should be recorded in the healthy volunteer's notes. New or worsened clinically significant abnormalities should be recorded as adverse events on the Adverse Event eCRF.

Height will only be recorded at Screening. Weight will be recorded at time-points for complete Physical Examination as specified in the SoA ([Appendix 1](#), [Appendix 2](#), [Appendix 3](#) and [Appendix 4](#)). BMI will be calculated at Screening in accordance with the formula provided in [Appendix 5](#).

#### **4.6.1.3 Vital Signs**

BP, pulse rate, respiratory rate and body temperature will be recorded at the time-points specified in the SoA ([Appendix 1](#), [Appendix 2](#), [Appendix 3](#) and [Appendix 4](#)).

BP, pulse rate and respiratory rate should be obtained in a quiet room at a comfortable temperature, with the healthy volunteer's arm unconstrained by clothing or other material. BP, respiratory rate and pulse rate will be obtained after the subject has been in a supine or sitting position for at least 5 minutes. All BP and pulse rate measurements will be obtained from the same arm (where possible), in the same position and with the same cuff size, using a well-calibrated automatic instrument with a digital readout, throughout the study. BP measurement will be performed in triplicate (can be as short as 20 second to 1 minute interval between measurements). The mean of three consecutive replicates will be used as the value for the defined time-point.

Body temperature measurement can be either oral or tympanic; the method should be maintained throughout the study.

#### **4.6.1.4 Electrocardiograms**

Triplet ECG recordings (i.e., three useful ECGs without artifacts) will be obtained within approximately 2-5 minutes at each specified time-point. The average of the three readings will be used to determine ECG intervals (PR [PQ], QRS, QT, QTcF). The intervals will be captured or calculated, and the changes in T-wave and U-wave morphology will be documented. T-wave information will be captured as normal or abnormal, U-wave information will be captured in two categories: absent/normal or abnormal.

Whenever possible, the same brand/model of a standard digital high-quality, high-fidelity electrocardiograph machine equipped with computer-based interval measurements should be used for each subject. The conditions should be as close as possible to pre-dose time-points; this includes but is not limited to food intake, activity level, stressors and room temperature.

To minimize variability, it is important that subjects be in a resting position for ≥ 10 minutes prior to each ECG evaluation. Body position should be consistently

maintained for each ECG evaluation to prevent changes in heart rate. Environmental distractions (e.g., television, radio, conversation) should be avoided during the pre-ECG resting period and during ECG recording. ECGs should be performed prior to any scheduled vital sign measurements and blood draws. In some cases, it may be appropriate to repeat abnormal ECGs to rule out improper lead placement as contributing to the ECG abnormality.

For safety monitoring purposes, the Investigator must review, sign and date all ECG tracings. Paper copies will be kept at the study centers with the subject's clinical file as part of the permanent record. The ECG intervals and interpretation will be recorded on the eCRF or may be sent electronically. If considered appropriate by Roche, ECGs may be analyzed retrospectively at a central laboratory.

If any ECG recording documents QT/QTc values > 500 msec or increases from Day -1 QTc > 60 msec (as provided by the machine), the site should repeat the ECG triplicate within the next 5 minutes and notify the Sponsor. If confirmed, ECG recordings should be repeated at least hourly until two successive ECGs show QTc values below the threshold value that triggered the repeated measurement.

